- Section 8: Table 8-1 was modified to replace MUGA scans with cardiac MRI scans throughout the study and remove chest X-ray at screening. HIV testing at screening if required by local requirements/regulations was added and table was modified to indicate at which visits cardiac Troponin is to be measured for the subjects
- Section 8.1 was updated to add flexibility for subjects to be re-screened once for criteria other than laboratory abnormalities and to clarify the rules for re-testing and re-screening.
- Section 8.4.1: Table 8-5 was updated to add testing of cTnT/TnI and possibility to perform local HIV testing when required per local regulations
- Section 8.4.2.1 was revised to replace MUGA scans with cardiac MRI scans
- Section 8.4.2.2 was added to described the troponin monitoring guideline
- Section 8.4.4 was revised to remove chest X-ray at screening
- Section 8.5.1: Table 8-7 and Table 8-8 were revised to be consistent with the footnotes and the dose ID numbers were modified in Table 8-7
- Section 9.1.4 was updated to clarify reasons for early termination to be consistent with the latest version of the Novartis Standard Language for Protocols
- Section 10.1.1 was updated to clarify that disease progression should be reported as an SAE if the investigator considers that progression of malignancy is accelerated by study treatment
- Section 15 was updated to include the references related to immune-mediated myocarditis and its management with glucocorticoids
- All the protocol including sections 1.1.3.2, 4.5.2, 6.1, 6.2 and 6.5 including Tables 6-3 to 6-10 was modified to be consistent with the latest version of the Novartis PDR001 compound Standard Language for Protocols
- In addition, revisions to the protocol were made to be consistent with the latest version of the Novartis Standard Language for Protocols and to correct typos including in section releated to protocol amendment 1 changes.

IRB Section

A copy of this amended protocol will be sent to the Institutional Review Board (IRBs)/Independent Ethics Committee (IECs) and Health Authorities.

[figure not shown]
The changes herein affect the Informed Consent. Sites are required to update and submit for approval a revised Informed Consent that takes into account the changes described in this protocol amendment.

Amendment 1 (18-Jun-2018)

Amendment rationale

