Visit Name	Screening	e 1	Cycl e 1 Day 15 Day 1 Da											day Safet y F-	End Post Treatme nt Follow- up	Surviv al F- up ⁴		
Days	-21 to -1	1	8 ±1	15 ±1	22 ±1	29 ±1	43 ±1	50 ±1	57 ±1	- ±3	-	- -0 +7	- ±7	- ±7	- ±7	- -0 +14	-	-
Tumor evaluation (CT scan/MRI/Bone scan)	-28 to -1	8-2 for	r imagir	weeks (+/- 1 week) for the first 9 months and every 12 weeks (+/- 1 week) thereafter, aging collection plan and Section 8.3.1. Upon the approval of amendment 4, the tumor assessments during the post-treatment efficacy period will be now optional and will be left at the discretion of the investigator.														
Chest X-ray		If clini	ically i	ndicate	ed													
ECG (Central)	At least 72 hours prior randomizati on	x					х				x							
ECG (Local)		s			s		s			On Day 1 of every 2 cycles after cycle 3								
Cardiac imaging (MRI/ECHO)	Х	If clini	linically indicated X															
Adverse Events			up to Day 150; non-suspected AE up to Day 150 or start of new post treatment anti-neoplastic medication, oner. See Appendix 1 (Safety follow-up diagram)															
Serious Adverse Events			to Day 150 and beyond; non-suspected SAE up to Day 150 or start of new post treatment anti-neoplastic medication, whichever is ndix 1 (Safety follow-up diagram)															

Novartis	Confidential	Page 86 of 185
Amended Protocol Version 04 (Clean)		Protocol No. CLAG525B2101

Period	Screening	Treat	ment								End of Treatment (EOT)	Follow	v-up³					
Visit Name	Screening	Cycl e 1 Day 1	Cycl e 1 Day 8	Cycl e 1 Day 15	Cycl e 2 Day 1	Cycl e 2 Day 8	Cycl e 3 Day 1	Cycl e 3 Day 8	e 3	Subseq. cycles Day 1	End of Treatment (EOT)	30 day Safet y F- up	60 day Safet y F- up	90 day Safet y F- up	120 day Safet y F- up	150 day Safet y F- up	End Post Treatme nt Follow- up	Surviv al F- up ⁴
Days	-21 to -1	1	8 ±1	15 ±1	22 ±1	29 ±1	43 ±1	50 ±1	57 ±1	- ±3	-	- -0 +7	- ±7	- ±7	- ±7	- -0 +14	-	-
Newly obtained tumor sample ²	Х																	
LAG525 infusion		Day 1	of eac	ch cycl	e (21 d	days) ι	ıntil EC	DΤ										

Period	Screening	Treat	ment								End of Treatment (EOT)	Follow	v-up³					
Visit Name	Screening	e 1	Cycl e 1 Day 8		e 2	e 2	e 3	e 3	Cycl e 3 Day 15	Subseq. cycles Day 1	End of Treatment (EOT)	30 day Safet y F- up	60 day Safet y F- up		120 day Safet y F- up	150 day Safet y F- up	End Post Treatme nt Follow- up	Surviv al F- up ⁴
Days	-21 to -1	1	8 ±1	15 ±1	22 ±1	29 ±1	43 ±1	50 ±1	57 ±1	- ±3	-	- -0 +7	- ±7	- ±7	- ±7	- -0 +14	-	-

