If a participant is known to have a contraindication to CT intravenous (IV) contrast media or develops a contraindication during the trial, a non-contrast CT of the chest (MRI is not recommended due to respiratory artifacts, however if CT is not feasible per local regulations, MRI can be performed instead) plus a contrast-enhanced MRI (if possible) of the abdomen and pelvis should be performed.

A whole body bone scan should be performed per institutional standard of care (e.g., Tc-99 bone scan, whole body bone MRI, Fluorodeoxyglucose positron emission tomography (FDG-PET) or sodium fluoride (NaF) PET). Localized CT, MRI or X-rays should be acquired for all skeletal lesions identified on the screening whole body bone scan, which are not visible on the chest, abdomen and pelvis CT/MRI.

If clinically indicated, CT or MRI of other areas (e.g., neck) of disease as appropriate should be performed.

Any potentially measurable lesion that has been previously treated with radiotherapy should be considered as a non-measurable lesion. However, if a lesion previously treated with radiotherapy has clearly progressed since the radiotherapy, it can be considered as a measurable lesion.

Chest x-rays and ultrasound should not be used to measure tumor lesions.

Post-baseline imaging assessments

Imaging assessments as described in Table 8-2 should be performed using the same imaging modality used at baseline, irrespective of study treatment interruption or actual dosing (see Table 8-1). Imaging assessments for response evaluation will be performed every 6 weeks (+/- 7 days) during the first 9 months, and every 12 weeks (+/- 7 days) thereafter as outlined below. Imaging assessments should be scheduled using the randomization date as the reference

date (not the date of the previous tumor assessment), and should be respected regardless of whether treatment with study treatment is temporarily withheld or unscheduled assessments performed.

Additional imaging assessments may be performed at any time during the study at the investigator's discretion to support the efficacy evaluations for a participant, as necessary. Clinical suspicion of disease progression at any time requires a physical examination and imaging assessments to be performed promptly rather than waiting for the next scheduled imaging assessment.

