8.4.2.1 Cardiac imaging - MRI or echocardiography (ECHO)

Cardiac imaging will be done at screening, during the study treatment period if clinically indicated and at the end of treatment visit.

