8.4.2.2 Troponin monitoring guidance

Cardiac enzyme troponin-T or I will be performed at screening. Troponin T assessment is recommended (Troponin I to be used if unable to assay TnT).

Additional safety assessments must be done during the first 2 months as outlined in Table 8-1. If Troponin level is above ULN during the first 2 months, or if level is above the screening value (if value was 1-2 fold ULN), echocardiogram and ECG must be performed. If ECG and ECHO are normal, Troponin must be repeated the following day. However if either ECG or ECHO are abnormal and suggestive of myocarditis, a cardiologist must be consulted.

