Shift tables using the low/normal/high/ (low and high) classification to compare baseline to the worst on-treatment value.

Other safety evaluations

Other safety data (e.g., cardiac imaging) will be summarized or listed as appropriate.

12.5.3 **Pharmacokinetics**

The respective PAS for each study drug will be used in the pharmacokinetic data analysis.

Drug concentration values below the lower limit of quantitation (LLOO) will be displayed in listings as zero with a flag and handled as zero in the calculations for mean, CV for mean, standard deviation, minimum, median, maximum, but handled as missing for the calculation of the geometric means and their CV.

Descriptive statistics (n, m (number of non-zero concentrations), mean, CV%, SD, median, geometric mean, geometric CV%, minimum and maximum) for spartalizumab, LAG525 and carboplatin concentrations will be presented at each scheduled timepoint and visit by treatment group.

All spartalizumab, LAG525 and carboplatin concentration data will be displayed graphically and by treatment group and visit.

PK parameters may be calculated using the PK sampling in cycle 1 and cycle 3, as appropriate. The descriptive statistics (n, mean, CV%, standard deviation (SD), median, geometric mean, geometric CV%, minimum and maximum) will be presented for all PK parameters for spartalizumab, LAG525 and carboplatin by treatment group for both cycle 1 and cycle 3 defined in Table 12-1 except Tmax, where only n, median, minimum and maximum will be presented.

Table 12-1	Non-compartmental pharmacokinetic parameters for spartalizumab, LAG525 and carboplatin
AUClast	The AUC from time zero to the last measurable concentration sampling time (tlast) (mass x time x volume-1)
AUCtau	The AUC calculated to the end of a dosing interval (tau) at steady-state (amount x time x volume-1)
Cmin or Ctrough	The minimum observed plasma or serum drug concentration (mass x volume-1)
Cmax	The maximum (peak) observed plasma, blood, serum, or other body fluid drug concentration after single dose administration (mass x volume-1)
Tmax	The time to reach maximum (peak) plasma, blood, serum, or other body fluid drug concentration after single dose administration (time)

[figure not shown]

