2.9.4 Other safety data

2.9.4.1 ECG and cardiac imaging data

At scheduled visits, triplicate 12-lead ECG's will be performed. ECG machines will automatically calculate heart rate and measures of PR, QRS, QT, and QTcF intervals. ECG data will be read and interpreted centrally.

Unscheduled safety ECG’s may be performed at the discretion of the investigator at any time during the study as clinically indicated. Unscheduled ECG’s with clinically significant findings should be collected in triplicate.

Clinically significant abnormalities observed from single 12-lead ECGs collected at the study site are not part of the data analysis described below, but must be reported as adverse events.

ECHO/MUGAs will be performed to assess cardiac ejection fraction. The same procedure (either ECHO or MUGA) should be performed at baseline, follow-up visits if clinically indicated, and at EOT. All ECHO/MUGA assessments will be read and interpreted locally.

Data handling

In case the study requires ECG replicates at any assessment, the average of the ECG parameters at that assessment should be used in the analyses.

Data analysis

The number and percentage of subjects with notable ECG values will be presented by treatment arm.

- QT, QTcF
 - New value of > 450 and ≤ 480 ms
 - New value of > 480 and ≤ 500 ms
 - New value of > 500 ms
 - Increase from Baseline of > 30 ms to ≤ 60ms
 - Increase from Baseline of > 60 ms
- HR
 - Increase from baseline >25% and to a value > 100 bpm
 - Decrease from baseline >25% and to a value < 50 bpm
- PR
 - Increase from baseline >25% and to a value > 200 ms
 - New value of > 200 ms
- QRS
 - Increase from baseline >25% and to a value > 120 ms
 - New values of QRS > 120 ms

A listing of all ECG assessments will be produced by treatment arm and notable values will be flagged. In the listing, the assessments collected during the post-treatment period will be flagged.

For left ventricular ejection fraction (LVEF), a shift table using CTC grades for 'Ejection fraction - decrease' as defined per CTCAE version 5.0 to compare baseline to the worst on-treatment value will be provided:

CTCAE	0	1	2	3	4
-------	---	---	---	---	---

Ejection fraction - decrease	-	-	Resting ejection fraction (EF) 50 - 40%; 10 - 19% drop from baseline	Resting ejection fraction (EF) 39 - 20%; $\geq 20\%$ drop from baseline	Resting ejection fraction (EF) $< 20\%$
------------------------------	---	---	--	---	---

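### The SAP's LVEF shift table assumes one imaging method per participant (ECHO or MUGA), but the protocol allows cardiac MRI or ECHO with no same-method rule, so a change of method could be graded as a change in LVEF, or could mask one.

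*Protocol*

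**What the plan says.** **Protocol.** Section 8.4.2.1 ("Cardiac imaging - MRI or echocardiography (ECHO") consists of one sentence, which sets timing only: "Cardiac imaging will be done at screening, during the study treatment period if clinically indicated and at the end of treatment visit". The Assessment Schedule (Table 8-1) has the matching row, "Cardiac imaging (MRI/ECHO". Neither place offers MUGA, and neither says that a participant stays on the screening method. The protocol does have a same-modality rule ("should be performed using the same imaging modality used at baseline"), but it stands in section 8.3.1 and governs tumor imaging. Section 8.4.2.2 says that, if troponin in the first two months exceeds the stated limits, "echocardiogram and ECG must be performed". It names echocardiography whatever method was used at screening. On analysis, section 12.5.2 says only: "Other safety data (e.g., cardiac imaging) will be summarized or listed as appropriate".

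**SAP.** Section 2.9.4.1 says that ejection fraction is assessed by ECHO or MUGA, read locally, and continues: "The same procedure (either ECHO or MUGA) should be performed at baseline, follow-up visits if clinically indicated, and at EOT". Cardiac MRI is not mentioned. The section then plans a shift table for LVEF using CTCAE v5.0 grades, baseline against worst on-treatment value. Grade 2 is a resting value of 50 to 40%, or a 10 to 19% drop from baseline. Grade 3 is a resting value of 39 to 20%, or a drop of 20% or more. The table carries no condition on imaging method. SAP section 1 states that the plan is based on protocol v04, so both texts are current.

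**The concern.** A drop from baseline is interpretable only if the two values come from comparable measurements. The SAP secures this by stating that one procedure is used throughout, but the protocol, which is what sites follow, does not deliver that premise. It offers a method that the SAP does not list, has no same-method rule, and can itself bring about a switch: a participant screened by MRI whose troponin rises must have an echocardiogram. Because the table takes the worst on-treatment value, one cross-method reading can set the reported grade.

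The participants moved to ECHO in this way are those with a possible cardiac signal. Amendment 2 added troponin monitoring because of an increased risk of potentially fatal autoimmune myocarditis seen in other sponsors' trials of anti-LAG-3 with PD-1 inhibitors. What is at stake is whether the LVEF table can be read at face value for those participants.

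**Working it through.** The plan gives no figure for this point, so there is nothing to reproduce. The check sets the texts side by side and then illustrates the size under stated assumptions.

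**1. Texts compared**

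| Item | Protocol v04 | SAP |
|---|---|---|
| Methods | MRI or ECHO (8.4.2.1, Table 8-1) | ECHO or MUGA (2.9.4.1) |
| Same method per participant | No rule for cardiac imaging | Stated, for ECHO and MUGA only |
| Raised troponin | ECHO required (8.4.2.2) | Not addressed |
| Analysis | Summarize or list (12.5.2) | Graded shift table, partly on drop from baseline |
| Change of method | Not addressed | Not addressed |

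Nothing elsewhere in the SAP fills the gap. The safety baseline in section 2.1.1 is the last available assessment on or before treatment start, with no reference to method. The tie-break rules there cover laboratory, ECG and vital-sign values. The local reading of images means that no central read harmonizes the methods.

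**2. Which pairs are affected**

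- MRI at screening and MRI later: permitted and comparable, so not affected.
- ECHO at screening and ECHO later: not affected.
- MRI at screening and ECHO later (for example, triggered by troponin), or any other switch: affected.

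**3. What an offset does to the grade**

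The documents give no between-method offset. Assume 5 points (range 0 to 10), and read the grade's percentage drop as LVEF points. Observed drop = true drop plus or minus the offset.

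- Later method reads lower: 5 + 5 = 10, so a true 5-point fall reaches the grade 2 drop limit.
- Later method reads higher: 14 − 5 = 9, so a true 14-point fall misses it.

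**4. How often a switch alone would reach the limit**

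Assume no true change, and an observed drop that is normal with mean b (the offset) and standard deviation s. Then P(drop ≥ 10) = 1 − Φ((10 − b)/s). For example, with b = 5 and s = 4, 1 − Φ(1.25) = 10.6%.

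| s (assumed) | b = 0 | b = 3 | b = 5 |
|---|---|---|---|
| 4 | 0.6% | 4.0% | 10.6% |
| 6 | 4.8% | 12.2% | 20.2% |
| 8 | 10.6% | 19.1% | 26.6% |

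The b = 0 column is what measurement noise alone would produce. The probability of reaching the grade 3 drop limit (20 points) is at most 3.0% in every cell.

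**5. How many participants**

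The documents give neither the share screened by MRI nor the share with a later value by another method; the count needs both. If 5 to 20% of the 88 randomized had an MRI baseline (assumed), that is 0.05 × 88 = 4.4 to 0.20 × 88 = 17.6 people. If 10% of those also had a later value by another method (assumed), the MRI-baseline cross-method pairs number 0.44 to 1.76. Switches from another baseline method would add to this by an unknown amount.

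**The case against.** The strongest reply is that this is an outdated modality name and little more. The shift table is defined for LVEF and is not limited by method, so an MRI value is not shut out, and MRI-to-MRI comparisons are sound. The table has no test or decision rule attached. Detection of myocarditis runs through troponin, ECG, ECHO and cardiology consultation (protocol 8.4.2.2), the myocarditis row of Table 6-10, and adverse event reporting. It does not depend on this table. All of that stands, and it limits the importance of the point.

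It does not dispose of it. The SAP chose a graded change-from-baseline table and rested it on a one-procedure premise that the protocol does not secure and that section 8.4.2.2 can break. The SAP's own same-procedure sentence does not help a participant whose baseline was an MRI, and a SAP cannot direct what sites collect.

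A reader might also infer that the SAP made an undeclared change to the protocol's analysis, since SAP section 4 reports none. That does not follow. Protocol 12.5.2 asks only that cardiac imaging be summarized or listed, and a shift table is consistent with that. Nor does the protocol itself name ejection fraction as the purpose of the imaging; that comes from the SAP.

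**Conclusion.** The mismatch between the two current documents is established. The LVEF shift table has no rule for pairs taken by different methods, so such a pair could have a method difference graded as an LVEF change, or a real change masked. The effect is confined to one descriptive safety table; ORR, the proof-of-preliminary-efficacy criteria and the sample size are untouched.

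Its size cannot be stated from the documents. The 5-point offset, the standard deviations, the MRI share and the switching rate are all assumptions, and if no participant changed method the table is unaffected. A reader might infer that every participant with an MRI baseline is affected, or falls outside the analysis. The documents do not support either reading: same-method MRI pairs are permitted and valid, and nothing in the table's definition excludes them.

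**What to change.** In SAP 2.9.4.1:

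- Add cardiac MRI to the list of methods. Keep MUGA: the Amendment 2 log records "Section 8.4.2.1 was revised to replace MUGA scans with cardiac MRI scans", and four participants had already been treated when that amendment was released, so MUGA baselines may exist.
- Base the drop-from-baseline grade in the main shift table on pairs taken by the same method.
- Show cross-method pairs separately, flagged by method, with both absolute LVEF and the observed change.

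Grading cross-method pairs on absolute LVEF alone would not be enough. With the same assumed 5-point offset, a true 53% reads as 53 − 5 = 48% and meets the grade 2 absolute limit. A fall from 68% to 54%, which is 14 points, would go ungraded because 54% lies above that limit. Showing both quantities avoids hiding a possible decline.

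Protocol 8.4.2.1 and 8.4.2.2 should be reconciled with the SAP's same-procedure statement. At Amendment 4, 85 of the 88 randomized had stopped treatment, so the practical gain lies in the SAP.

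The cost is a wording correction, one derivation condition and one extra display. A few participants would move from the main shift table to the flagged display.

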8.4.2.2 Troponin monitoring guidance

Cardiac enzyme troponin-T or I will be performed at screening. Troponin T assessment is recommended (Troponin I to be used if unable to assay TnT).

Additional safety assessments must be done during the first 2 months as outlined in Table 8-1. If Troponin level is above ULN during the first 2 months, or if level is above the screening value (if value was 1-2 fold ULN), echocardiogram and ECG must be performed. If ECG and ECHO are normal, Troponin must be repeated the following day. However if either ECG or ECHO are abnormal and suggestive of myocarditis, a cardiologist must be consulted.

8.4.3 Pregnancy and assessments of fertility

A condom is required for all sexually active male participants treated with carboplatin (Arm 2 and Arm 3) to prevent them from fathering a child AND to prevent delivery of study treatment via seminal fluid to their partner. In addition, male participants should not donate sperm for the time period as defined per exclusion criteria 24 (Section 5).

All premenopausal women who are not surgically sterile will have pregnancy testing as follows. Additional pregnancy testing might be performed if requested by local requirements.

- At screening, a serum pregnancy testing will be performed within 72 hours of first dose of study treatment on all female participants of childbearing potential as defined per exclusion criteria 25.
- During study treatment, urine pregnancy tests will be performed on Day 1 of each cycle at the clinic/investigator's site. Any positive urine test needs to be confirmed with a serum test. If positive, the participant must be discontinued from the study treatment.
- At end of treatment visit, 30day and 150day safety follow-up visits, a serum pregnancy test will be performed.

Assessments of Fertility

Medical documentation of oophorectomy, hysterectomy, or tubal ligation must be retained as source documents. Subsequent hormone level assessment to confirm the woman is not of child bearing potential must also be available as source documentation in the following case:

1. Surgical bilateral oophorectomy without a hysterectomy

In the absence of the above medical documentation, follicle stimulating hormone (FSH) testing is required of any female participant, regardless of reported reproductive/menopausal status at screening/baseline.

